2.6 Hypotheses and Research Questions

[figure not shown]
1. What is the acceptability of mHealth among YLWH at three (03) of Kiryandongo District HIV Centres, and what are the barriers, facilitators/enablers of ART and clinic visit adherence?

Hypothesis: YLWH will have a high acceptability for mHealth with 70% accepting to use mHealth.

2. What is the effect of the mHealth-CFLU tool on ART adherence among YLWH?

Hypothesis: More than 79% of YLWH using the mHealth-CFLU tool will be adherent to ART (using viral load suppression as a proxy measure for ART adherence we anticipate an increment of 15%).

3. What is the cost of the mHealth CFLU intervention compared to standard of care over a 12 month period?

Hypothesis: mHealth will be cost effective by increasing proportion in care and proportion with viral suppression compared to standard of care

CHAPTER THREE: METHODS

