3.2 Study setting

The study will be based at three HIV care and treatment centres in Kiryandongo District (fig 4).

Kiryandongo District has 19 government health units (one hospital, 5 Health Centre IIIs and 13 Health Centre II) which serve a population over 317,500 people. The study sites will include Kiryandongo Hospital ART clinic, Panyadoli Health Centre III and Nyakadote Health Centre (HCII). Kiryandongo is located 225 km on the Kampala –Gulu highway, with a viral load suppression prevalence of 55.3% (UPHIA, 2017). Kiryandongo hospital has been chosen as the study site, because it is an IDI implementing site with >1000 YLWH in care and a viral suppression rate of 79% below the UNAIDS target of 90% (Table 1). In 2018, a total of 637 youths were enrolled in care and retention in care was 79%. The current total of YLWH at the site is 1,322. The two government centres Panyadoli and Nyakadot are 44 mins /19 mins drive from Kiryandongo hospital which 30 KM and 16 KM from the Hospital. The HCIII serves a population of over 80,000 people and are included as they serve a big population of youth living with HIV in the district.

Fig 4. Map of Uganda showing Kiryandongo District

[figure not shown]
[figure not shown]
[figure not shown]

Fig 4: Snap shot of Kiryandongo district with the 3 study sites (Kiryandongo Hospital, Nyakadoti Health Centre II and Panyadoli Health Centre III)

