To assess effect of mHealth tool (CFLU) on ART adherence and knowledge of COVID-19 among YLWH naïve, initiating ART or on ART since Jun 2019.

RESEARCH & ETHICS COMMITTEE
[name]

Study design: Randomized control trial with 2 arms (Standard of Care or CFLU with Standard of Care)

Study purpose: To assess effect of CFLU on ART adherence among youth measured by interactive voice response to daily adherence calls mapped in the database and proportion with viral suppression of copies below 1000 copies/mL.

The intervention (CFLU) uses IVR calls or text messages delivered via MOTECH™ based Connect for Life technology™. The calls are delivered in 3 languages (Luganda, English and Runyakitara) and the participant has to make a choice of the preferred language during registration to the system. The system offers adherence pill reminders, health message tips, visit appointment reminders and receipt of self-reported symptoms.

A poor understanding of the disease among youths can result in delayed identification and treatment leading to rapid spread of infections among the community.

Study setting: Kiryandongo District, 3 sites offering HIV-ART. Kiryandongo hospital, Panyandoli Health Centre III and Nyakadote Health Centre II have been chosen as the study sites, the hospital has 1,322 YLWH and a viral suppression rate of 79% (Table 1). In 2018, a total of 637 YLWH were enrolled in care. By Jun 2019 and additional 218 YLWH had been enrolled in care. The current total at the site for age between 15-24 is 1,322. Overall retention was 79%. We have included the lower level health facilities since ART delivery is done majorly in these grassroot levels.

Study Population: Inclusion: YLWH (15-24 years), ART naïve or initiating ART since Jun 2019.

Exclusion: Hearing loss, severe illness likely to shorten life span, boarding school YLWH, Inability to use a basic mobile phone.

Sample size calculation:

Sample Size: X-Sectional, Cohort, & Randomized Clinical Trials (Kelsey et al., Methods in Observational Epidemiology 2nd Edition, Table 12-15; Fleiss, Statistical Methods for Rates and Proportions, formulas 3.18 & 3.19)

The sample size formula for the method described in Kelsey et. al. is:

$$n_1 = \frac{(Z_{\alpha/2} + Z_{1-\beta})^2 \bar{p} \bar{q} (r+1)}{r(p_1 - p_2)^2}$$

[figure not shown]
and

$$n_2 = rn_1$$

where

n_1 = number of cases in the intervention

n_2 = number of controls

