$Z_{\alpha/2}$ = standard normal deviate for two-tailed test based on alpha level (relates to the confidence interval level)

Z_{β} = standard normal deviate for one-tailed test based on beta level (relates to the power level)

r = ratio of controls to cases

p_1 = proportion of cases with exposure and $q_1 = 1-p_1$

p_2 = proportion of controls with exposure and $q_2 = 1-p_2$

$$\bar{p} = \frac{p_1 + rp_2}{r+1} \quad \text{and} \quad \bar{q} = 1 - \bar{p}$$

The sample size formula *without* the correction factor by Fleiss is:

$$n_{\text{UC}} = \frac{n_1}{4} \left[1 + \sqrt{1 + \frac{2(r+1)}{n_1 \tau |p_2 - p_1|}} \right]$$

[figure not shown]
$$n_{\text{2x}} = r n_{\text{UC}}$$

When the input is provided as an odds ratio (OR) rather than the proportion of cases exposed, the proportion of cases exposed is calculated as:

$$p_1 = \frac{p_2 \text{OR}}{1 + p_2(\text{OR} - 1)}$$

Sample Size: X-Sectional, Cohort, & Randomized Clinical Trials (OpenEpi, 2019) (<https://www.openepi.com/SampleSize/SSCohort.htm>)

Two-sided significance level (1- α):	95
Power (1- β , % chance of detecting):	80
Ratio of sample size, Unexposed/Exposed:	1
Percent of Unexposed with Outcome:	79
Percent of Exposed with Outcome:	94 (Jessica E. Haberer et al., 2013)
Odds Ratio:	4.2
Prevalence Ratio:	1.2
Prevalence difference:	15

	Kelsey	Fleiss	Fleiss with CC
Sample size- Exposed(intervention):	81	80	93
Sample Size-Nonexposed (Control):	81	80	93
Total Sample Size:	162	160	186

CC= continuity correction. Results are rounded up to the nearest integer.

Calculation output:

[Expand All](#) | [Collapse](#)

- [Home](#)
- [Info and Help](#)
- [Language/Options/Settings](#)
- [Calculator](#)
- [Counts](#)
 - [Std.Mort.Ratio](#)
 - [Proportion](#)
 - [Two by Two Table](#)
 - [Dose-Response](#)
 - [R by C Table](#)
 - [Matched Case Control](#)
 - [Screening](#)
- [Person Time](#)
 - [1 Rate](#)
 - [Compare 2 Rates](#)
- [Continuous Variables](#)
 - [Mean CI](#)
 - [Median/Percentile CI](#)
 - [t test](#)
 - [ANOVA](#)
- [Sample Size](#)
 - [Proportion](#)
 - [Unmatched CC](#)
 - [Cohort/RCT](#)
 - [Mean Difference](#)
- [Power](#)
 - [Random numbers](#)
- [Searches](#)
 - [Google--Internet](#)
 - [PubMed--MEDLARS](#)
 - [Internet Links](#)
 - [Download OpenEpi](#)
- [Development](#)

[Start](#) | [Enter](#) | [Help](#) | [Examples](#)

Sample Size:X-Sectional, Cohort, & Randomized Clinical Trials

Two-sided significance level(1-alpha):	95
Power(1-beta, % chance of detecting):	80

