Central 1	64.2	56.7-72.6
Central 2	56.9	49.1-64.5
Kampala	62.1	53.4-70.7
East-Central	48.8	42.3-55.2
Mid-East	52.9	45.4-61.4
North-East	70.0	60.4-79.5
West Nile	60.5	50.5-70.5
Mid-North	54.6	45.4-63.7
Mid-West	55.3	46.1-64.4
South-West	68.0	60.2-75.7
Overall	59.6	56.8-62.5

[figure not shown]
[figure not shown]

TABLE 1: Viral suppression among YLWH enrolled at Kiryandongo Hospital

Currently in Care

TX_CURR Dec 2017			TX_CURR Dec 18			TX_CURR Jun19			
15-19Yrs	20-24Yrs	TOTAL	15-19Yrs	20-24Yrs	TOTAL	15-19Yrs	20-24Yrs	TOTAL	
Total	413	761	1174	451	857	1308	506	816	1322

New in Care

TX_NEW Jan to Dec 17			TX_NEW Jan to Dec 18			TX_NEW Jan to June 19			
15-19Yrs	20-24Yrs	TOTAL	15-19Yrs	20-24Yrs	TOTAL	15-19Yrs	20-24Yrs	TOTAL	
Total	64	232	296	148	489	637	49	169	218

Viral Suppression

Period	Valid Results	Suppressed Results	Non Suppressed Results	Suppression Rate (%)
Dec-17	414	298	116	72%
Dec-18	466	368	98	79%
Jun-19	260	208	52	80%

Retention over all at the site

	Dec-17			Oct to Dec 2018			
	12 Months			12 Months			
Organisation unit	Net Current Cohort	%age retained		Net Current Cohort	%age retained		
TOTAL	282	76%		266	79%		

[figure not shown]
[figure not shown]
[figure not shown]

FIGURE7: CALL FOR LIFE UGANDA- FUNCTIONALITY MODULES (INTERVENTION TO BE USED)

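### Hypothesis 2 is worded as a bar on CFLU users alone, set at the assumed control rate, although the trial is a two-arm randomised comparison and the analysis section names no between-arm test

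*Combined protocol and SAP*

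**What the plan says.** Question 2 in section 2.6 asks for the effect of the tool on ART adherence. The hypothesis beneath it is "Hypothesis: More than 79% of YLWH using the mHealth-CFLU tool will be adherent to ART". A parenthesis in the same sentence adds "using viral load suppression as a proxy measure for ART adherence we anticipate an increment of 15" per cent.

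Section 3.4, Study Objective 2, gives the design as "Randomized control trial with 2 arms (Standard of Care or CFLU with Standard of Care"). The sample size there is a two-proportion comparison: "Percent of Unexposed with Outcome: 79", 94 for the exposed, a difference of 15, "Two-sided significance level (1- α): 95" and "Power (1- β , % chance of detecting): 80". It arrives at 93 per arm, raised to 103 per arm (206 in all) for 10% loss to follow-up.

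The 79% is the hospital's 2018 figure. Section 3.2 describes the hospital as having "a viral suppression rate of 79% below the UNAIDS target of 90" per cent. Table 1 gives 298/414 (72%) for December 2017, 368/466 (79%) for December 2018 and, for June 2019, "Jun-19 260 208 52 80" per cent.

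On analysis, the Data Management Analysis Plan provides for time-to-suppression curves in both arms. The Bivariate Analysis lists age, gender, ART duration, marital status, education, occupation and religion. The Multivariate Analysis is a logistic regression for factors that influence adherence, suppression and retention. Under Study Objective 3, the numbers suppressed at months 6 and 12 are to be compared across arms, with no test named.

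**The concern.** The effect of an intervention is a contrast between arms. A threshold applied to one arm measures the background rate and the effect together, and cannot separate them. Here the threshold equals the rate the plan itself expects without CFLU. Taken at its word, the hypothesis could be supported when both arms do equally well, or when CFLU does worse than standard of care.

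A second ambiguity is the word for tool users. It may simply mean the CFLU arm. It could also be read as those who engaged with the tool, a group formed after randomisation. Section 3.6 foresees non-use through blocked PINs, SIM swapping and parental restriction.

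Loose wording in a hypothesis is usually harmless because the analysis section fixes the comparison. In this plan it does not, so a reader who looks for the planned test of CFLU finds only this sentence and the sample size.

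**Working it through.** **1. The plan's own figure.** Inputs from section 3.4: p1 = 0.94, p2 = 0.79, two-sided 5%, power 80%, ratio 1, mean proportion 0.865.
- Kelsey: (1.960 + 0.842)² × 0.865 × 0.135 × 2 / 0.15² = 81.5 per arm (stated 81).
- Fleiss, uncorrected: 80.3 (stated 80).
- Fleiss with continuity correction: 93.1 (stated 93).
- Loss to follow-up: 186 / 0.9 = 206.7 (stated 206).

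All agree to within one per arm after rounding. The trial is sized as a two-arm comparison of 79% with 94%.

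**2. Table 1 rates.** 298/414 = 72.0%; 368/466 = 79.0%; 208/260 = 80.0%.

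**3. Chance of passing the literal bar with no CFLU effect.** The plan states no such rule; this only measures what the sentence would mean if applied as written. If the intervention arm has n participants with results and true rate p, the chance is P(X/n > 0.79), with X binomial(n, p).
- n = 93: 0.79 × 93 = 73.47, so at least 74 suppressed.
- n = 103: 0.79 × 103 = 81.37, so at least 82 suppressed.

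| True rate, both arms | n = 93 | n = 103 |
|---|---|---|
| 72% | 6.2% | 5.0% |
| 79% | 50.7% | 49.7% |
| 80% | 60.2% | 59.7% |

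The no-effect rate in the trial population is not given. The range 72-80% is an assumption taken from Table 1.

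**4. How firm is the June 2019 rate?** The difference from December 2018 is 80.0 − 79.0 = 1.0 point. Its standard error is √(0.80 × 0.20/260 + 0.79 × 0.21/466) = 3.1 points. The 95% interval for 208/260 is 80.0 ± 1.96 × 2.48, about 75% to 85%.

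**5. Does the analysis section supply the contrast?** Side by side:
- Curves of time to suppression are drawn for both arms, but no test or effect measure between arms is named.
- Randomised arm is not among the listed independent variables.
- Suppression is compared across arms only under the cost objective, at two time points, with no test named.

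No primary between-arm comparison of suppression is specified.

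**The case against.** The strongest reply is that the intention is plain. The same sentence anticipates a 15% increment, and an increment needs a reference. The sample size supplies it: 79% unexposed, 94% exposed, two-sided. Hypothesis 3 in the same section speaks of suppression relative to standard of care. Section 2.6 lists informal research hypotheses; Hypothesis 1 also uses a bare percentage. This stands, and it rules out reading the trial as a single-arm design.

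Two stronger readings are tempting and should be resisted.
- A reader might infer that passing 79% is the trial's success criterion, or that results will be tested against the 2018 rate. Nothing in the document calls it a criterion or plans a one-sample or historical comparison.
- A reader might infer from Table 1 that the hospital had already passed the bar by June 2019. A one-point gap with a standard error of about three points does not show that. Both rates also come from one of three sites, and the trial admits ART-naive youth.

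The engagement cut-offs in the protocol apply to the end-of-study focus groups, so the wording about users is an ambiguity and not a declared subset analysis. Arm could also enter the logistic model through the clause admitting variables with a scientific explanation.

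The reply does not remove the point. The increment has no stated reference in section 2.6, and is not said to be relative or absolute. The sentence holds two different bars: a result of 85% passes 79% but falls short of 94%. A clause that would permit arm in a model is not a prespecified primary comparison.

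**Conclusion.** The point holds as a defect in the stated hypothesis. Hypothesis 2 sets an absolute bar, equal to the planned control rate, on CFLU users alone, where the question and the design call for a randomised contrast. Taken literally, it would be met with no effect about half the time at a true rate of 79%, about 60% of the time at 80%, and only 5-6% of the time at 72%. These figures assume 93 to 103 results in the CFLU arm and a background rate within the hospital's Table 1 range; the rate across the three trial sites is unknown. That uncertainty is itself a reason to rely on the concurrent control arm already in the design.

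The design and sample size are two-arm and need no change on this account. The wording deserves correction because the analysis section names no between-arm test of suppression that would override it.

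**What to change.** In section 2.6, replace Hypothesis 2 with: *the proportion with viral load <1000 copies/mL at [month 6 or month 12, one to be named] will be higher in youth randomised to CFLU plus SoC than in youth randomised to SoC alone; the trial is sized to detect 79% v 94%.* This deletes the bar of more than 79% and replaces users of the tool with those randomised to it.

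In the analysis section of 3.4, state the same comparison as the primary analysis: suppression by randomised arm at the named time point, with the test and effect measure given. Editing section 2.6 alone would leave the main gap open.

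The cost is one sentence in section 2.6 and a short statement in the analysis section, made by amendment before the arms are compared. No additional data, visits or participants are needed, because viral load is already collected at baseline and months 6 and 12.

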3.1 Study Design: Mixed Methods Sequential study

[figure not shown]
The study design is a mixed method sequential, where the qualitative study will be done first, followed by the randomized controlled trial and thereafter the cost evaluation study.

3.2 Study setting

The study will be based at three HIV care and treatment centres in Kiryandongo District (fig 4).

Kiryandongo District has 19 government health units (one hospital, 5 Health Centre IIIs and 13 Health Centre II) which serve a population over 317,500 people. The study sites will include Kiryandongo Hospital ART clinic, Panyadoli Health Centre III and Nyakadote Health Centre (HCII). Kiryandongo is located 225 km on the Kampala –Gulu highway, with a viral load suppression prevalence of 55.3% (UPHIA, 2017). Kiryandongo hospital has been chosen as the study site, because it is an IDI implementing site with >1000 YLWH in care and a viral suppression rate of 79% below the UNAIDS target of 90% (Table 1). In 2018, a total of 637 youths were enrolled in care and retention in care was 79%. The current total of YLWH at the site is 1,322. The two government centres Panyadoli and Nyakadot are 44 mins /19 mins drive from Kiryandongo hospital which 30 KM and 16 KM from the Hospital. The HCIII serves a population of over 80,000 people and are included as they serve a big population of youth living with HIV in the district.

Fig 4. Map of Uganda showing Kiryandongo District

[figure not shown]
[figure not shown]
[figure not shown]

Fig 4: Snap shot of Kiryandongo district with the 3 study sites (Kiryandongo Hospital, Nyakadoti Health Centre II and Panyadoli Health Centre III)

3.3 Study population

The study population will comprise of YLWH aged 15 -24 years who are ART naïve or on ART since Jun 2019.

Target population:

Youth living with HIV registered to receive ART at any of the 3 ART clinic in Kiryandongo district :Kiryandongo Hospital, Panyandoli HCIII and Nyakadoti HCII

Accessible population:

[figure not shown]
Youths consented/assented for CFLU, registered for care at Kiryandongo hospital, Panyadoli HCIII or Nyakadoti CII.

3.4 Materials and Methods

Study Objectives:

1a: To assess barriers, enablers of adherence among youth living with HIV in Kiryandongo at baseline and study end.

1b: To assess acceptability of mHealth among youth living with HIV in Kiryandongo at baseline and study end.

Study design: Qualitative study with narrative approach

Study purpose: To identify the key behavioral constructs that enable or hinder ART adherence among the youths, and to assess acceptability of mHealth interventions for adherence support.

Study population: YLWH 15-24 years attending Kiryandongo Hospital, Panyadoli Health Centre III or Nyakadote Health Centre II HIV/ART clinic, ART naïve or on ART since Jun 2019.

Sampling: Participants will be purposively selected, each group will include 6-10 YWLH, and there will be a total of 3-5 groups ((Morgan, 1992). The participant groups will comprise of those who are naïve or initiating and on ART since Jun 2019. YWLH will be stratified by age group (≤ 18 ys and > 18 ys) and gender.

Study Procedure:

Selection criteria:

Inclusion: Youth living with HIV, with a documented HIV test result, aged 15-24 yrs, ART naïve or on ART since Jun 2019.

Exclusion Criteria: Youth unable to express themselves verbally, those unable to attend 2 sessions of the discussion

Selection of participants: We shall liaise with the clinic counsellor to refer YLWH aged 15-24 years with a documented HIV test result, patients who are ART naïve or initiating ART and have gone through routine counselling and testing. Stratification by age group and gender will be

[figure not shown]
considered in selection of study participants. Eligible youth will be identified by the clinic counsellor and will be referred to study team which will be located at the HIV clinic. We shall sit one on one with the potential participant, give information about the purpose of the study, and request them to join the focus group discussion on the scheduled date if they agree to take part. This procedure will be repeated until the sample size of a particular group is reached.

Sample Size: Focus group discussions will be held until data saturation is achieved.

Data Collection:

[figure not shown]
Focus group discussions: On the day of the discussion, study information will be given to the participant including the purpose of the study, risks and benefits. We will address any questions they may have and obtain consent. An experienced person (Social Sciences group at the Academy) in conducting FGDs will facilitate the discussion assisted by two note takers (the PI and a research assistant). Ground rules will be set and choice of languages to use will be Runyoro, Kiswahili and English which are the dominant languages at the site. FGDs have been preferred and not in-depth interviews, because this study is generating information on collective views which will be used for later, and we want to generate a rich understanding of the youths experiences and beliefs (Gill, Stewart, Treasure, & Chadwick, 2008).

At baseline, we will administer an interview guide consisting of structured questions on the CFLU mHealth tool and ART adherence, as well as open-ended qualitative questions with probes, to allow exploration of YLWH views and opinions regarding these themes. The key issues to be explored are whether the youth would accept or refuse use of an mHealth tool, what they would/ wouldn't like the system to offer in terms of health education, frequency and timing of pill reminders and why. Regarding ART adherence, ART naïve participants will be asked what factors will likely facilitate / hinder their adherence to clinic attendance and ART. ART exposed participants will be asked what has facilitated or hindered their clinic attendance and ART adherence. The FGD will last for about 40 to 45 minutes. It will be audio recorded and refreshments (light snack and a soft drink) will be served. Themes to be assessed at baseline include acceptability of mHealth, assessing knowledge, usage, specifics needed, frequency timing.

[figure not shown]

At the end of the study, the groups will be subdivided according to the themes of acceptability and adherence. For acceptability, further segmentation will be based on those who have utilized the mHealth tool above or below 75% of times. For ART adherence, we shall subgroup according to viral suppression (VL <1000 or >1000 copies/mL), gender and age-group below or above 18 years. The FGD guide (appendix IV) will explore the different barriers and enablers for adherence, and the responses to mHealth intervention. The discussion will be captured on an audio recorder and handwritten notes.

Data collection for the FGD at study entry, before randomisation:

Themes		ART experienced (on ART 3months and above)		Less experienced (less than 3months) and ART Naive	
		Male		Female	
		≤18 yrs	>18 yrs	≤18 yrs	> 18yrs
Acceptability:					
Why accept or refuse mHealth					
How can the system be used for adherence (probe on time, frequency)?					
What they would like the system to do for them(Probe on pill reminders, Health tips/advice , symptom reporting and management and use of secret pin)					
Adherence:					
Enablers/barriers:					
(what has facilitated/hindered for those who are ART experienced)					
(what will likely facilitate- for those who are naïve or less experienced					

Data collection for the FGD at study end; groups will be divided according to how well they interacted with mHealth tool (> 50% ≤50%), age group (>18yrs ≤18yrs) and sex (male or female)

Themes	Groups			
	≤50% interaction/engagement with tool		(>50% interaction/engagement with tool)	
	Male		Female	
	≤18yrs	> 18yrs	≤18yrs	> 18yrs
Acceptability: Comfort/ease using the tool Following advice from Health tips Likes/dislikes for tool Improvements & recommendations				
Adherence: Enablers (what has facilitated) Barriers(What has hindered)			 
MAKERERE UNIVERSITY SCHOOL OF MEDICINE RENEWAL VALID UNTIL ★ 10 FEB 2023 ★ RESEARCH & ETHICS COMMITTEE [name]
	

[figure not shown]
Data Management and analysis:

The FGD audio-recordings will be translated and transcribed into English by a group of 4 qualitative research assistants from the Academy at Infectious Diseases Institute. Transcripts will be read, to identify themes and subthemes. Themes will be discussed, coded and the coded book with the transcripts will be imported to Nvivo for coding and content analysis. The analysis will be done by the qualitative social sciences Lead from the Academy at IDI. Audio files will be electronically stored in password protected files which will only be accessible to the study team.

The analysis will be guided by the themes already contained in the interview guide, which will further be refined following multiple readings of interview scripts to better understand the data, identify sub-themes and to group the data according to themes for analysis and interpretation. Quotations reflecting the youths' views, opinions and experiences will be identified and will be used in the presentation of study findings.

Study Objective 2:

To assess effect of mHealth tool (CFLU) on ART adherence and knowledge of COVID-19 among YLWH naïve, initiating ART or on ART since Jun 2019.

RESEARCH & ETHICS COMMITTEE
[name]

Study design: Randomized control trial with 2 arms (Standard of Care or CFLU with Standard of Care)

Study purpose: To assess effect of CFLU on ART adherence among youth measured by interactive voice response to daily adherence calls mapped in the database and proportion with viral suppression of copies below 1000 copies/mL.

The intervention (CFLU) uses IVR calls or text messages delivered via MOTECH™ based Connect for Life technology™. The calls are delivered in 3 languages (Luganda, English and Runyakitara) and the participant has to make a choice of the preferred language during registration to the system. The system offers adherence pill reminders, health message tips, visit appointment reminders and receipt of self-reported symptoms.

A poor understanding of the disease among youths can result in delayed identification and treatment leading to rapid spread of infections among the community.

Study setting: Kiryandongo District, 3 sites offering HIV-ART. Kiryandongo hospital, Panyandoli Health Centre III and Nyakadote Health Centre II have been chosen as the study sites, the hospital has 1,322 YLWH and a viral suppression rate of 79% (Table 1). In 2018, a total of 637 YLWH were enrolled in care. By Jun 2019 and additional 218 YLWH had been enrolled in care. The current total at the site for age between 15-24 is 1,322. Overall retention was 79%. We have included the lower level health facilities since ART delivery is done majorly in these grassroot levels.

Study Population: Inclusion: YLWH (15-24 years), ART naïve or initiating ART since Jun 2019.

Exclusion: Hearing loss, severe illness likely to shorten life span, boarding school YLWH, Inability to use a basic mobile phone.

Sample size calculation:

Sample Size: X-Sectional, Cohort, & Randomized Clinical Trials (Kelsey et al., Methods in Observational Epidemiology 2nd Edition, Table 12-15; Fleiss, Statistical Methods for Rates and Proportions, formulas 3.18 & 3.19)

The sample size formula for the method described in Kelsey et. al. is:

$$n_1 = \frac{(Z_{\alpha/2} + Z_{1-\beta})^2 \bar{p} \bar{q} (r+1)}{r(p_1 - p_2)^2}$$

[figure not shown]
and

$$n_2 = rn_1$$

where

n_1 = number of cases in the intervention

n_2 = number of controls

$Z_{\alpha/2}$ = standard normal deviate for two-tailed test based on alpha level (relates to the confidence interval level)

Z_{β} = standard normal deviate for one-tailed test based on beta level (relates to the power level)

r = ratio of controls to cases

p_1 = proportion of cases with exposure and $q_1 = 1-p_1$

p_2 = proportion of controls with exposure and $q_2 = 1-p_2$

$$\bar{p} = \frac{p_1 + rp_2}{r+1} \quad \text{and} \quad \bar{q} = 1 - \bar{p}$$

The sample size formula *without* the correction factor by Fleiss is:

$$n_{\text{UC}} = \frac{n_1}{4} \left[1 + \sqrt{1 + \frac{2(r+1)}{n_1 \tau |p_2 - p_1|}} \right]$$

[figure not shown]
$$n_{\text{2x}} = r n_{\text{UC}}$$

When the input is provided as an odds ratio (OR) rather than the proportion of cases exposed, the proportion of cases exposed is calculated as:

$$p_1 = \frac{p_2 \text{OR}}{1 + p_2(\text{OR} - 1)}$$

Sample Size: X-Sectional, Cohort, & Randomized Clinical Trials (OpenEpi, 2019) (<https://www.openepi.com/SampleSize/SSCohort.htm>)

Two-sided significance level (1- α):	95
Power (1- β , % chance of detecting):	80
Ratio of sample size, Unexposed/Exposed:	1
Percent of Unexposed with Outcome:	79
Percent of Exposed with Outcome:	94 (Jessica E. Haberer et al., 2013)
Odds Ratio:	4.2
Prevalence Ratio:	1.2
Prevalence difference:	15

	Kelsey	Fleiss	Fleiss with CC
Sample size- Exposed(intervention):	81	80	93
Sample Size-Nonexposed (Control):	81	80	93
Total Sample Size:	162	160	186

CC= continuity correction. Results are rounded up to the nearest integer.

Calculation output:

[Expand All](#) | [Collapse](#)

- [Home](#)
- [Info and Help](#)
- [Language/Options/Settings](#)
- [Calculator](#)
- [Counts](#)
 - [Std.Mort.Ratio](#)
 - [Proportion](#)
 - [Two by Two Table](#)
 - [Dose-Response](#)
 - [R by C Table](#)
 - [Matched Case Control](#)
 - [Screening](#)
- [Person Time](#)
 - [1 Rate](#)
 - [Compare 2 Rates](#)
- [Continuous Variables](#)
 - [Mean CI](#)
 - [Median/Percentile CI](#)
 - [t test](#)
 - [ANOVA](#)
- [Sample Size](#)
 - [Proportion](#)
 - [Unmatched CC](#)
 - [Cohort/RCT](#)
 - [Mean Difference](#)
- [Power](#)
 - [Random numbers](#)
- [Searches](#)
 - [Google--Internet](#)
 - [PubMed--MEDLARS](#)
 - [Internet Links](#)
 - [Download OpenEpi](#)
- [Development](#)

[Start](#) | [Enter](#) | [Help](#) | [Examples](#)

Sample Size:X-Sectional, Cohort, & Randomized Clinical Trials

Two-sided significance level(1-alpha):	95
Power(1-beta, % chance of detecting):	80
Ratio of sample size. Unexposed/Exposed:	1
Percent of Unexposed with Outcome:	79
Percent of Exposed with Outcome:	94
Odds Ratio:	4.2
Risk/Prevalence Ratio:	1.2
Risk/Prevalence difference:	15

	Kelsey	Fleiss	Fleiss with CC
Sample Size - Exposed	81	80	93
Sample Size-Noneexposed	81	80	93
Total sample size:	162	160	186

References

Kelsey et al., Methods in Observational Epidemiology 2nd Edition, Table 12-15
 Fleiss, Statistical Methods for Rates and Proportions, formulas 3.18 & 3.19
 CC = continuity correction
 Results are rounded up to the nearest integer.
 Print from the browser menu or select, copy, and paste to other programs.

Results from OpenEpi, Version 3, open source calculator--SSCohort
 Print from the browser with ctrl-P
 or select text to copy and paste to other programs.

MAKERERE UNIVERSITY
 SCHOOL OF MEDICINE
 RENEWAL
 VALID UNTIL

★ 10 FEB 2023 ★

RESEARCH & ETHICS COMMITTEE
 103 FOR EACH ARM, KAMPALA

Factoring 10% loss to follow-up, the total sample size will be 206(103 for each arm, KAMPALA)

[figure not shown]
Data collection procedures:

The intervention is mobile phone based IVR. However, the CLFU trial found that, it was observed that a good number of participants (50 of 256) at the urban site were not enrolled due to absence of a basic mobile phone, or had malfunctioning phone keyboards (for Poster Exhibition at the 20th International Conference on AIDS and STIs in Africa (ICASA 2019). Therefore, we shall provide a basic mobile phone to everyone in the study (SoC and intervention arm). To avoid stigma associated with a particular phone, we shall get 4 or more types of basic phones. Issues regarding simcard registration will be dealt with by the individuals.

Four study questionnaires will be administered at baseline and 6-monthly until the 12-month exit visit.

The questionnaires will capture:

- Sociodemographic and medical history
- Stigma scores
- Knowledge assessment
- Sexual behavior assessment
- Knowledge of COVID-19 (only at baseline)

The data will be entered using REDCap. Blood for viral load will be collected at baseline and at the 6 and 12-month visit.

Intervention: mHealth CFLU tool

The tool capitalises on a basic mobile phone's core utilities of voice and short messaging services. The system design, development, testing and evaluation was done by Janssen and the Grameen Foundation (<http://motechsuite.org/index.php/implementations>). In 2015, Janssen Global Public Health Research and Development, in close collaboration with the Infectious Diseases Institute Kampala (IDI), developed Call for Life Uganda (CFLU) tailored to the needs of PLHIV in Uganda. The CFLU system follows the Health Insurance Portability and Accountability Act (HIPAA) Privacy and Security rules. While the Privacy rules deals with electronic Protected Health Information, the security rule covers administrative, physical and technical safeguards to ensure confidentiality, integrity and security of electronic protected health information. Data transaction between patient and system is encrypted when it comes to human subjects. The system is password protected, and interaction of system and patient is personalised with a secret code. The system interacts with the patient through a basic mobile phone via a keypad and with the health worker through a web-based interface. The system has options to either use interactive voice response or short message service and the user has to make a choice, get a secret pin code which ensures privacy to enduser.

Screening-Enrolment procedures:

All potential participants will be written on the screening log, and a screening form completed, reasons for screen failure will be documented on the screening log. Following successful screening, the participant will be referred to the Research Assistant (RA) to receive a

thorough explanation of the study so and informed consent is obtained. The RA then administers the stigma questionnaire along with the sociodemographic and medical information, , HIV knowledge and sexual behaviour questionnaires. A client locator form will be completed which will help in physical contact tracing, and the participant will be registered on the enrolment log.

Randomisation will follow (see details of randomisation procedure below) thereafter and the result in the sealed envelope will dictate whether the patient will be registered onto the Call for Life System for the intervention or continue with standard of care as per MoH HIV Management guidelines.

Registration onto the CFLU system: Refer to Standard operating procedures on registration. However, all patients will be registered onto the electronic and hard copy of the enrolment log and a next appointment date is given to them. Finally, the lab request forms are filled and the patient sent for a blood draw. The patient returns from the lab, receives their transport refund of UGX 20,000, with a basic mobile phone (only at baseline visit, to all participants) and is allowed to go home.

No intervention: Standard of care arm

[figure not shown]
The Ministry of Health developed a minimum healthcare services package for PLHIV to standardize the programming, implementation and delivery of integrated HIV services in Uganda

The standard of care arm is based on the Apr 2018, consolidated guidelines for prevention and treatment of HIV in Uganda (MoH, 2018), and will also follow the healthcare services package for PLHIV (U. MoH, September 2014).

The SOC arm will follow the services below:

- Care and support for people living with HIV, and the first line ART regimen is TDF/3TC/DTG
- First-Line Regimen for Adults and Adolescents aged above 10 Initiating ART:

Preferred First-Line Regimen: TDF+3TC+DTG All HIV-infected adults and adolescents aged 10 years and above should be initiated on tenofovir, lamivudine and dolutegravir (TDF+3TC+DTG) as a once-daily fixed dose combination. When to use TDF+3TC+EFV: Adults and adolescents aged 10 years and above should only be initiated on TDF+3TC+EFV if their weight does not allow for use of the currently available DTG formulations (containing 50mg). Note: DTG 50mg

should only be given to adults and adolescents weighing 40kg and above. When the 10mg and 25mg formulations become available, DTG will be administered to children and adolescents weighing less than 40kg.

- When to use ABC+3TC+DTG:

Adults and adolescents aged 10 years and above should only be initiated on ABC+3TC+DTG if TDF is contraindicated, including the following conditions:

1. Kidney disease and estimated glomerular filtration rate (GFR) below 60 ml/min
2. Adolescents below 35 kg of weight.

- Adherence Preparation, Monitoring, And Support:

The study team will use the 5 As principles for chronic care as a guide to offer pre-ART adherence counselling and psychosocial support. These are Assess, Advise, Agree, Assist and Arrange. The youths will be followed-up every 6 months as per MoH guidelines.

